6.1 Study treatment

Details on the requirements for storage and management of study treatment, and instructions to be followed for prescribing/dispensing, and administering study treatment are outlined in the pharmacy manual.

6.1.1 Investigational and control drugs

Commercially Confidential Information

The investigational drug, MAS825 and the matching placebo will be prepared by Novartis and supplied as open labeled bulk medication to the unblinded site pharmacist ([Table 6-1](#)). An unblinded pharmacist or authorized designee is required to dispense the study drug.

Commercially Confidential Information

Table 6-1 Investigational and control drug

Investigational/ Control Drug (Name and Strength)	Pharmaceutical Dosage Form	Route of Administration	Supply Type	Sponsor (global or local)
MAS825 CCI	Commercially Confidential Information	Intravenous use	Commercially Confidential Information	

Investigational/ Control Drug (Name and Strength)	Pharmaceutical Dosage Form	Route of Administration	Supply Type	Sponsor (global or local)
Matching Placebo	Concentrate for solution for infusion	Intravenous use	Open label bulk supply; vials	Sponsor (global)

6.1.2 Additional study treatments

Patients assigned to the MAS825 arm will receive single dose of MAS825 CCI i.v. in addition to SoC, and patients assigned to the control arm will receive matching placebo in addition to SoC. Administered SoC in addition to study treatment will be supplied by the investigational site. No other investigational treatment beyond MAS825 is included in this study.

6.1.3 Treatment arms/group

Participants will be assigned at randomization to one of the following treatment arms/groups in a ratio of 1:1:

- MAS825 CCI i.v.
- Matching placebo i.v.

6.2 Other treatment(s)

6.2.1 Concomitant therapy

All medications, procedures, and significant non-drug therapies (including physical therapy and blood transfusions) administered after the participant was enrolled into the study must be recorded on the appropriate Case Report Forms (CRF).

Each concomitant drug must be individually assessed against all exclusion criteria/prohibited medication. If in doubt, the investigator should contact the Novartis medical monitor before randomizing a participant or allowing a new medication to be started. If the participant is already enrolled, contact Novartis to determine if the participant should continue participation in the study.

If participants are discharged from hospital prior to Day 15, they must be told to notify the treating physician about any new medications he / she takes after receiving MAS825 treatment.

During the course of the study and also prior to screening, participants may receive anti-viral therapies (e.g., hydroxychloroquine, chloroquine, remdesivir, faripivavir, ritonavir, lopinavir convalescent plasma containing high titres of anti SARS-CoV-2 antibodies), intravenous, oral or inhaled corticosteroids (e.g. prednisolone, dexamethasone, methylprednisolone), antibiotics, anti-coagulants and other agents/treatments where these form part of SoC for the treatment of COVID-19 at their participating center (per medical judgement).

Patients are permitted to receive low-dose corticosteroids (up to a maximum of 10 mg/day prednisolone equivalent) for the treatment of non-COVID-19 disorders. Immunomodulatory (topical or inhaled) use for asthma and atopic dermatitis or corticosteroid use (per medical judgement) are not restricted.

Whilst the protocol defines experimental immunomodulatory treatments including but not limited to anti-IL-6 monoclonal antibodies as prohibited ([Section 6.2.1.1](#)), patients with significantly deteriorating clinical status after MAS825 or placebo may still receive such therapies in rescue situations where their treating physician is of the opinion that the potential benefit of such therapy outweighs the risks. However, patients having received experimental immunomodulatory therapies as rescue therapy after treatment with MAS825 or placebo should remain in the study and the Investigator should continue collecting data on outcomes through the study visit schedule.

6.2.1.1 Prohibited drugs

The following medications are prohibited:

Experimental immunomodulatory therapies for the treatment of COVID-19, including, but not limited to canakinumab, anakinra and other anti-IL-1 antibodies, tocilizumab, sarilumab and other anti-IL-6 antibodies, ruxolitinib and other JAK inhibitors, eculizumab and other complement inhibitors (investigational or marketed).

Concomitant use of biologics including abatacept, rilonacept, rituximab and any other biologics (investigational or marketed) and TNF inhibitors including etanercept, adalimumab, infliximab and/or other TNF inhibitors (investigational or marketed).

All investigational medications being used in an investigational trial.

6.2.1.2 Permitted concomitant therapy requiring caution and/or action

Use of oral, injected or implanted hormonal methods of contraception are allowed while on MAS825.

6.3 Participant numbering, treatment assignment, randomization

6.3.1 Participant numbering

Each participant is identified in the study by a Participant Number (Participant No.), that is assigned when the participant is enrolled for screening and is retained for the participant throughout his/her participation in the trial. A new Participant No. will be assigned at every subsequent enrollment if the participant is re-screened. The Participant No. consists of the Center Number (Center No.) (as assigned by Novartis to the investigative site) with a sequential participant number suffixed to it, so that each participant's participation is numbered uniquely across the entire database. Upon signing the informed consent form, the participant is assigned to the next sequential Participant No. available.

A new ICF will need to be signed if the investigator chooses to re-screen the participant after a participant has screen failed, and the participant will be assigned a new Participant No.

6.3.2 Treatment assignment, randomization

At randomization visit, all eligible participants will be randomized via Interactive Response Technology (IRT) to one of the treatment arms. The investigator or his/her delegate will contact the IRT after confirming that the participant fulfills all the inclusion/exclusion criteria. The IRT

will assign a randomization number to the participant, which will be used to link the participant to a treatment arm.

The randomization numbers will be generated using the following procedure to ensure that treatment assignment is unbiased and concealed from participants and investigator staff. A participant randomization list will be produced by the IRT provider using a validated system that automates the random assignment of participant numbers to randomization numbers. These randomization numbers are linked to the different treatment arms. A randomization list will be produced by or under the responsibility of Novartis Global Clinical Supply (GCS) using a validated system that automates the random assignment of treatment arms to randomization numbers in the specified ratio.

Randomization will be stratified by:

- age (≤ 65 years, > 65 years)
- administration of any anti-viral therapy (e.g., hydroxychloroquine, chloroquine, convalescent plasma, remdesivir, faripivavir, ritonavir, lopinavir) as SoC (yes / no)
- presence of ≥ 1 of the following comorbidities: diabetes, hypertension, cardiovascular disease, chronic lung disease (yes / no)

The randomization scheme for participants will be reviewed and approved by a member of the Randomization Office.

6.4 Treatment blinding

This is a blinded study. Participants and investigators will remain blinded to study treatment throughout the study, except where indicated below.

Participants, investigator staff, persons performing the assessments, and the clinical trial team (CTT) will remain blind to the identity of the treatment from the time of randomization until end of study visit applying the following rules:

- Randomization data are kept strictly confidential until the time of unblinding.
- Unblinding will occur in the case of participant emergencies and at the conclusion of the study.
- Unblinding of the CTT members may occur for the purpose of periodic review of the safety data.
- Unblinded results from the planned interim analysis after all participants have completed the Day 29 visit can be shared with the participants and site staff, if deemed appropriate.

The identity of the treatments will be concealed by the use of study drugs that are all identical in packaging, labeling, schedule of administration, appearance, and odor.

Site staff

With the exception of any unblinded site staff identified below, all site staff (including study investigator and study nurse) will be blinded to study treatment throughout the study.

Unblinding a single participant at site for safety reasons (necessary for participant management) will occur via an emergency system in place at the site.

Drug product will be supplied in bulk, so an unblinded pharmacist who is independent of the study team will be required in order to maintain the blind. This unblinded pharmacist at the site will be notified by the IRT system that a participants randomized and to which treatment arm, which will then enable them to prepare the study drug. Appropriate measures must be taken by the unblinded pharmacist to ensure that the treatment assignments are concealed from the rest of the site staff.

Sponsor staff

The following unblinded sponsor roles are required for this study amend as appropriate:

- Unblinded field monitor(s)
- Unblinded clinical staff managing drug re-supply to site
- Unblinded sample analyst(s) CCI

Commercially Confidential Information

The unblinded field monitors are required to review drug accountability and allocation at site. The unblinded monitors are not provided with a randomization list directly but will be unblinded through review of source documentation compiled by the unblinded pharmacist, which details treatment allocation to individual participants.

Sponsor clinical staff are required to assist in the management and re-supply of investigational drug product. These individuals are not provided with randomization lists directly, but may be unblinded through communication of drug re-supply needs via the unblinded site pharmacists.

The sample analysts will receive a copy of the randomization schedule (via request to the Randomization Office), to facilitate analysis of the samples. The sample analysts will provide the sample data to the study team under blinded conditions unless otherwise allowed.

The study statistician will be able to access the randomization list for interim analyses and is allowed to share unblinded information with the rest of the clinical team as appropriate for internal decision purposes, as outlined in [Table 6-2](#). For example, unblinded summaries and unblinded individual data can be shared with the team for all interim analyses.

Study programmers and other personnel involved in study data analysis CCI are allowed to access treatment assignment information for the purpose of conducting interim analyses.

The clinical trial team is allowed to share unblinded results with other sponsor staff (e.g. decision boards) as required for internal decision making on the study or the project at the time of interim analyses while the study is ongoing. The results from the planned interim analysis after all participants have completed their Day 29 visit (or discontinued from the study earlier) can be shared more broadly including with participants and site staff, if deemed appropriate. If this occurs, then all roles should be considered unblinded from this time points onwards. Otherwise, following final database lock all roles may be considered unblinded.

All unblinded personnel will otherwise keep randomization data or information that could unblind other study team members confidential and secure except as described above.

Table 6-2 Blinding and unblinding plan

Role	Time or Event			
	Randomization list generated	Treatment allocation & dosing	Safety event (single participant unblinded)	Interim analysis
Participants	B	B	UI	B*
Site staff	B	B	UI	B*
Unblinded site staff e.g. pharmacy staff (specify)	UI	UI	UI	UI
Global Clinical Supply and Randomization Office	UI	UI	UI	UI
Unblinded sponsor staff e.g. for study treatment re-supply, unblinded monitor(s), sample analyst(s)	UI	UI	UI	UI
Unblinded Pharmacovigilance sponsor staff	UI	UI	UI	UI
Statistician/statistical programmer/ data analysts (e.g. CCI)	B	B	UI	UI
Independent committees used for assessing interim results, if required (e.g. DMC)	B	B	UI	UI
All other sponsor staff not identified above (i.e. trial team, project team, management & decision boards, support functions)	B	B	UI	UI

UI: Allowed to be unblinded on individual participant level

B: Remains blinded

NA: Not applicable to this study

* Unblinded results from the planned interim analysis after all subjects have completed their Day 29 visit (or discontinued earlier) can be shared with participants and site staff, if deemed appropriate. Results from any other interim analysis prior to the Day 29 visit should not be shared with participants and site staff.

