12. Women of child-bearing potential, defined as all women physiologically capable of becoming pregnant, **unless** they agree to abstain from any sexual intercourse for a total of 29 days after randomization (the 14-day treatment period plus a 14-day follow-up period). During the safety follow up (from day 29 onwards), WOCBP should practice highly effective contraception for 4 months following treatment with MAS825, when it is predicted that IL-18 and IL-1 β will not be neutralized by MAS825.

Women are considered post-menopausal and not of child bearing potential if they have had 12 months of natural (spontaneous) amenorrhea with an appropriate clinical profile (e.g. age appropriate history of vasomotor symptoms) or have had surgical bilateral oophorectomy (with or without hysterectomy), total hysterectomy or bilateral tubal ligation at least six weeks prior to randomization. In the case of oophorectomy alone, only when the reproductive status of the women has been confirmed by follow up hormone level assessment is she considered not of child bearing potential.

13. Current participation in any other investigational trials, with the exception of (not yet) approved COVID-19 therapies that are considered (local) standard of care (also see [Section 6.2.1.1.](#) for Prohibited drugs).

6 Treatment

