2. Dose Reduced/increased
3. Drug interrupted/withdrawn

6. Its outcome (i.e., recovery status or whether it was fatal)

Conditions that were already present at the time of informed consent should be recorded in medical history of the participant.

Adverse events (including lab abnormalities that constitute AEs) should be described using a diagnosis whenever possible, rather than individual underlying signs and symptoms.

Adverse event monitoring should be continued until the end of study.

Once an adverse event is detected, it must be followed until its resolution or until it is judged to be permanent (e.g., continuing at the end of the study), and assessment must be made at each visit (or more frequently, if necessary) of any changes in severity, the suspected relationship to the interventions required to treat it, and the outcome.

Information about adverse drug reactions for the investigational drug can be found in the IB.

Abnormal laboratory values or test results constitute AEs only if they fulfill at least one of the following criteria:

- 1) they induce clinical signs or symptoms
- 2) they are considered clinically significant
- 3) they require therapy

Clinically significant abnormal laboratory values or test results must be identified through a review of values outside of normal ranges/clinically notable ranges, significant changes from baseline or the previous visit, or values which are considered to be non-typical in participant with the underlying disease.

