7.2 Descriptive analyses

Safety summaries (tables, figures) include only data from the on-treatment period with the exception of baseline data, which will also be summarized where appropriate (e.g. change from baseline summaries).

The on-treatment period lasts from the date of administration of study treatment to Day 127.

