7.2.6 Adverse events

All information obtained on adverse events will be listed by treatment and subject.

Summary tables for adverse events (AEs) will summarize only on-treatment events, with a start date during the on-treatment period (treatment-emergent AEs).

The number and percentage of subjects with adverse events will be tabulated by body system and preferred term with a breakdown by treatment. Separate summaries will be provided for study medication related adverse events and other significant adverse events leading to discontinuation.

The number of deaths resulting from SAEs suspected to be related to study treatment and SAEs irrespective of study treatment relationship will be provided by SOC and PT until day 29 and after day 29.

The number of deaths resulting from SAEs suspected to be related to study treatment and SAEs irrespective of study treatment relationship will be provided by PT until day 29 and after day 29.

A subject with multiple adverse events within a body system is only counted once towards the total of this body system and treatment.

For the legal requirements of ClinicalTrials.gov and EudraCT, two tables are required:

on treatment emergent adverse events which are not serious adverse events and on treatment emergent serious adverse events and SAE suspected to be related to study treatment will be provided by system organ class and preferred term on the safety analysis set.

If for a same patient, several consecutive AEs (irrespective of study treatment causality, seriousness and severity) occurred with the same SOC and PT:

- a single occurrence will be counted if there is ≤ 1 day gap between the end date of the preceding AE and the start date of the consecutive AE
- more than one occurrence will be counted if there is > 1 day gap between the end date of the preceding AE and the start date of the consecutive AE.

For occurrence, the presence of at least one SAE / SAE suspected to be related to study treatment / non SAE has to be checked in a block e.g., among AE's in a ≤ 1 day gap block, if at least one SAE is occurring, then one occurrence is calculated for that SAE.

The SAEs and deaths by State will be graphically presented in a barchart. Refer to [Section 10.8](#) for details on the state.

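### The protocol lets Day 29 interim results reach sites and participants without saying whether individual allocations are included; if they are, adverse events still being collected to Day 127 become open-label and are pooled with blinded data.

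*Protocol*

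**What the plan says.** Protocol section 6.4 opens with a general rule that carries an exception: "Participants and investigators will remain blinded to study treatment throughout the study, except where indicated below". One listed exception is: "Unblinded results from the planned interim analysis after all participants have completed the Day 29 visit can be shared with the participants and site staff", subject to this being judged appropriate. The sponsor-staff part of 6.4 repeats the permission, and adds: "If this occurs, then all roles should be considered unblinded from this time points onwards". The Table 6-2 footnote gives the permission a third time and bars sharing the results of any earlier interim analysis with participants and sites.

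Safety follow-up continues beyond that point. Protocol section 10.1.1 says: "Adverse event monitoring should be continued until the end of study". The same section requires a severity grade and a judgement of relationship to study treatment for each event. Section 10.1.3 requires SAE reporting up to the last study visit, which is Day 127 and is held by telephone for discharged participants.

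SAP section 7.2 says: "The on-treatment period lasts from the date of administration of study treatment to Day 127". SAP section 7.2.6 tabulates adverse events by treatment over that period and adds: "Separate summaries will be provided for study medication related adverse events and other significant adverse events leading to discontinuation". Deaths from SAEs are the only item it splits, at Day 29.

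**The concern.** Safety against placebo is a stated secondary objective (Protocol Table 2-1). While sites and participants are blind, both arms share the same reporting behaviour and the same standard for attributing an event to study treatment. If a site learns an individual allocation, it has little reason to suspect study treatment in a participant known to have had placebo. A participant who knows they received MAS825 may report more. Late events in discharged participants rest largely on telephone contact, so they are sensitive to this knowledge. The readable text describes no blinded assessor of causality.

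The SAP would place such events in the same tables as those collected blind. Its Day 29 split does not separate the two kinds of data: it covers deaths only, and it follows each participant's study day rather than the calendar date of release. An arm difference in late non-fatal events, or in related events, could then partly reflect knowledge of treatment.

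**Working it through.** The plan gives no figure on this point. Its primary power statement (60 per group, difference 3.6, SD 9.2, one-sided 10%) reproduces at 80.6% against 80% stated and is not affected.

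**Step 1: what level of release is meant?**

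- *Pointing to group results.* All three statements of the permission speak of results. Table 6-2 codes participants and site staff as B* at the interim analysis, and B means remaining blinded. Where section 6.4 intends individual data for the sponsor team, it says so.
- *Pointing to individual allocations.* After sharing, every role is treated as unblinded, and the only unblinded state in the Table 6-2 legend is "UI: Allowed to be unblinded on individual participant level".

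The text supports both readings and does not settle the matter.

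**Step 2: which data are exposed, if allocations are released?** The interim analysis follows the last participant's Day 29 (or earlier discontinuation). APACHE II at Day 15 or discharge and the Day 15 and Day 29 ordinal-scale endpoints are therefore already collected. Exposed are non-fatal adverse events, SAEs and causality judgements arising after release in participants short of Day 127.

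**Step 3: how much follow-up is that?**

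Inputs: Day 29 and Day 127 (Protocol section 3), so 127 − 29 = 98 days remain after Day 29. Enrolment duration E and lag L from the last participant's Day 29 to release are not in the readable documents, so both are assumed. Enrolment is taken as uniform; visit windows, deaths and withdrawals are ignored.

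A participant enrolled at time t, with t between 0 and E, has max(0, 98 − L − (E − t)) days left at release. Averaging over t and dividing by 98 gives the open-label share of Day 30–127 person-time:

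- if E ≤ 98 − L: (98 − L − E/2) / 98
- if E > 98 − L: (98 − L)² / (2 × E × 98)

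Examples: E = 60, L = 14 gives (84 − 30)/98 = 54/98 = 55%. E = 120, L = 14 gives 84²/(2 × 120 × 98) = 7056/23520 = 30%. E = 60, L = 60 gives 38²/(2 × 60 × 98) = 1444/11760 = 12%.

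| Lag L (days) | E = 60 | E = 120 | E = 180 | E = 360 |
|---|---|---|---|---|
| 14 | 55% | 30% | 20% | 10% |
| 28 | 41% | 21% | 14% | 7% |
| 60 | 12% | 6% | 4% | 2% |
| 90 | 0.5% | 0.3% | 0.2% | 0.1% |

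The share of participants still in follow-up at release is min(1, (98 − L)/E). For E = 60, 120, 180 and 360 this is 100%, 70%, 47% and 23% with L = 14, and 63%, 32%, 21% and 11% with L = 60.

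**Step 4: can the analysis separate the two kinds of data?** The readable SAP plans no unblinding-date flag and no table limited to the blinded period. However, Protocol section 10.1.1 requires start and end dates for each event, and SAP section 7.2.6 lists all events by treatment and subject. Given the release date, events with onset before it can be tabulated separately.

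**The case against.** The strongest case on the other side is that only group results may be meant, in which case most of the problem disappears. Release is also optional and openly planned under a stated exception, and prompt disclosure to participants in a pandemic trial is a legitimate choice. Questioning must be non-directive, the adverse event analysis is descriptive, and the occurrence of death is insensitive to reporting. Protocol section 4.5 and SAP sections 2 and 3 are blacked out and may give the timing, reason and level of disclosure.

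Much of this stands: the point is a conditional risk confined to late safety data. It does not remove the ambiguity in the open text. Non-directive questioning limits leading questions, but it blinds neither the participant's reporting nor the site's causality judgement.

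A reader might infer more than the documents support:

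- *That the protocol plainly authorises release of individual codes.* This has to be inferred from the statement about all roles and from the single unblinded code, against the wording on results and the B* entries.
- *That 98 days of follow-up would be open-label for the last participant.* This needs zero lag, but an interim analysis must come first.
- *That cytokine neutralisation is predicted to last about 4 months, so late harms are expected in Days 30–127.* Section 5.2 says "WOCBP should practice highly effective contraception for 4 months following treatment with MAS825", and gives that as the time by which neutralisation is predicted to be absent. It is an outer bound.
- *That blinded and open-label data could never be separated.* Event start dates allow it. What cannot be recovered is a blinded report or judgement of an event after release.

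**Conclusion.** The point holds as an ambiguity with a conditional consequence. Sections 6.4 and Table 6-2 leave open whether sites and participants may learn individual allocations before Day 127. If they do, later non-fatal adverse events, SAEs and attributions become open-label, and the SAP as readable pools them with blinded data.

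The size cannot be fixed from the documents. Under uniform enrolment over 60 to 360 days it runs from 55% of Day 30–127 person-time (fast enrolment, 14-day lag) to under 1% (90-day lag). These are shares of follow-up time exposed, not estimates of bias. The efficacy conclusions are untouched, and the comparison of events with onset before release can be kept. The change is worth making because it costs little and protects the late placebo-controlled safety comparison.

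**What to change.** **Protocol.** In both places in section 6.4 and in the Table 6-2 footnote, state that only group-level interim results may go to sites and participants before a participant's Day 127 contact or earlier study exit. Limit the sentence that treats all roles as unblinded to sponsor roles. Leave emergency unblinding as written.

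**SAP section 7.2.6.** If any site or participant is unblinded earlier, record the date. Tabulate adverse events, SAEs and treatment-related events with onset before and after that date separately. Base the between-arm comparison on the blinded period and show the full-period tables alongside.

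**Cost.** Wording changes, one date flag and some extra tables, with no added participants or visits. Some participants would learn their allocation later, by less than 98 days; group results could still be shared at once.
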